9.2.4.1 Efficacy Analyses

The data will be summarized with descriptive statistics, including Demographics, baseline, and each efficacy endpoint. The measurement data will be described by its mean, standard deviation, minimum, and maximum, and the 95% confidence interval for the mean will be calculated. The enumeration data will be described by its frequency and percentage, and the 95% confidence interval of the percentage will be calculated.

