Short Title	Phase II ^b Efficacy and Safety Evaluation of TC Cream in Treating Patients with Psoriasis Vulgaris.																				
Protocol Number	105883-1																				
Clinical Trial Phase	Phase II ^b																				
IND Sponsor	Psoriasis Research Institute of Guangzhou, Guangdong, China																				
Study Centers	Multi-centers: (1) (2)																				
Primary Objective	To observe the efficacy and safety of TC Cream twice daily compared to placebo over 8 weeks in subjects of US population with stable psoriasis.																				
Secondary Objectives	To evaluate the effects and improvements of TC Cream on the quality of life in subjects with psoriasis vulgaris (stable stage) based on Psoriasis Disability Index (PDI) and Dermatology Life Quality Index (DLQI); and to determine whether there is further improvement or recurrence of psoriasis after the cessation of TC Cream after 8 weeks treatment of psoriasis vulgaris of stable stage.																				
Exploratory Objectives	To investigate and summarize the curative effects and recurrence rate of TC Cream on treated psoriasis patients of US population																				
Sample Size	Total: 88 Subjects (44 for the treatment group and 44 for the control group) 
  
 Clinical centers	Stable Stage	Total	
 
 Arm 1 TC	Arm 2 Vehicle	
   
 Center 1				
 
 Center 2				
 
 Total				
  
			Clinical centers	Stable Stage		Total	Arm 1 TC	Arm 2 Vehicle	Center 1				Center 2				Total			
Clinical centers	Stable Stage		Total																		
	Arm 1 TC	Arm 2 Vehicle																			
Center 1																					
Center 2																					
Total																					
Study Population	Male or female patients of 18-70 years old of any race with psoriasis vulgaris of stable stage																				
Duration of Administration	8 weeks																				
Washout	4 weeks for any topical or systemic corticosteroids, anti-inflammatories, antibiotics, 3-months for any systemic retinoids or biologics, or any investigational treatment																				

Protocol Version: 00

period	
Duration of Study	6 months

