	
 ○ Any types of investigational therapy for psoriasis within the last 30 days ✓ Within 3 months prior to randomization the patients have taken systemic treatment with retinoids or biological therapies (marketed or others) with a possible effect on psoriasis (e.g., alefacept, efalizumab, etanercept, infliximab). ✓ Planned initiation of, or changes to, concomitant medication that could affect psoriasis (e.g., beta blockers, anti-malaria drugs, lithium) during the double-blind phase of the study.
Endpoints	
Observation of Curative Effects:
 
 (1) Severity of local signs - Phenotypes 
 a. Induration (average over all lesions) b. Erythema (average over all lesions) c. Scaling (average over all lesions) (2) Extent - Body Surface Area (BSA) affected (3) Symptoms - Pruritus/itching (average over 24 hours) (4) Visual assessment: Digital photographs on the target skin lesion 
Note: (1) All patients will be examined and photographed before (first visit) and after (end of the curative treatment) treatment with TC Cream or placebo.
 
(2) The investigator(s) can, not must, consider enrolling the patients may have a lesion on elbow and/or knee. However, the patients who have no lesion on elbow or knee or only have a lesion on one of parts can be enrolled into this research.
 
Outcome Measures:
 
 • Primary Endpoint: 
 (1) Investigator's Static Global Assessment (ISGA) (2) Assessment of Targeted Lesions • Secondary Endpoint: 
 (1) PASI \geq 75% improvement • Tertiary Endpoint: 
 (1) Psoriasis Disability Index (PDI) (2) Dermatology Life Quality Index (DLQI) 
Statistical Analysis:
 
Comparison between two groups will be made using the t-test with two-sided 95% confidence interval (CI) for the difference in response rates between the two treatment groups (ITT, TC vs. Vehicle). A P-value < 0.05 is considered to be statistically significant.
 
Frequency of Evaluation:
 
 – 0 (before treatments), 2, 4, 6 and 8 weeks – After the initial 8 weeks of treatment, there will be a follow up period of 4 weeks during which no treatment is used.

Schematic Flow of Study Design

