1.5.2 Toxicology

2. OBJECTIVES

- To observe the efficacy and safety of TC Cream twice daily compared to placebo over 8 weeks in subjects of the US population of patients with psoriasis vulgaris (stable stage) based on Investigator's Static Global Assessment (ISGA), Target Lesion, Psoriasis Area and Severity Index (PASI).
- To evaluate the effects and improvements of TC Cream on the quality of life in subjects with psoriasis vulgaris based on Psoriasis Disability Index (PDI) and Dermatology Life Quality Index (DLQI), and to determine whether there is further improvement or recurrence of psoriasis after the cessation of TC Cream after 8 weeks of treatment for psoriasis.
- To investigate and summarize the curative effect and recurrence rate of TC Cream on treated psoriasis patients of the US population.

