
5. MEASUREMENT OF EFFECT

5.1 Clinical End Points

Clinical outcomes will be evaluated by following the criteria:

1. Primary Endpoint:
 - (1) Investigator's Static Global Assessment (ISGA)
 - (2) Assessment of Target Lesions
2. Secondary Endpoint:
 - (1) PASI \geq 75% improvement
3. Tertiary Endpoint:
 - (1) Psoriasis Disability Index (PDI)
 - (2) Dermatology Life Quality Index (DLQI).

For the purposes of this study, patients should be evaluated at baseline (0) and reevaluated for response at 2, 4, 6, and 8 weeks. In addition, a rebound evaluation should also be obtained 4 weeks after the final evaluation of week 8.

The efficacy evaluation of all outcomes will be static ordinal, integer-valued, and scaled (e.g., success or failure), where 'success' involves a score of Clear/Almost Clear and a 2-grade improvement.

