9.2.4 Analysis Plan

The response to treatment with TC Cream will be assessed using an intention-to-treat (ITT) comparison with the placebo group (ratio of efficacy goals achieved).

The statistical analysis will be performed using a two-sided t-test with a 95% confidence interval (CI) for the difference in response rates between the two treatment groups (ITT, TC vs. Vehicle). A P value < 0.05 is considered to be statistically significant.

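### PDI and DLQI, tertiary endpoints that serve the secondary quality-of-life objective, have no usable between-arm comparison; a pre-specified week-8 ANCOVA would supply one

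*Combined protocol and SAP*

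**What the plan says.** - **Objective.** Section 2 sets out "To evaluate the effects and improvements of TC Cream on the quality of life in subjects with psoriasis vulgaris", measured by PDI and DLQI. The synopsis lists this under secondary objectives.
- **Endpoint rank.** The synopsis and section 5.1 both place PDI and DLQI in the tertiary tier, below ISGA, target lesions and PASI 75.
- **Scales.** Section 5.1.4 describes two PDI scorings, a visual analogue version (0 to 90) and a tick-box version (0 to 45), and does not choose between them. Section 5.1.5 gives DLQI as a total from 0 to 30, with descriptive impact bands. Neither section defines a responder.
- **Between-arm method.** Section 9.2.4 specifies a "two-sided t-test with a 95% confidence interval (CI) for the difference in response rates between the two treatment groups". The synopsis has the same scope: "Comparison between two groups will be made using the t-test with two-sided 95% confidence interval (CI) for the difference in response rates".
- **Measurement data.** Section 9.2.4.1 says "The measurement data will be described by its mean, standard deviation, minimum, and maximum", and adds a 95% interval for the mean. It does not mention a difference between arms.
- **Success rule.** Section 5.1 says that all outcomes are evaluated on an ordinal or success/failure basis. It defines success as reaching one of the two clearest grades together with a two-grade drop.
- **Timing.** Section 5.1 calls for evaluation at baseline, at weeks 2, 4, 6 and 8, and again 4 weeks after week 8. It does not name instruments by visit, and the schedule in section 4.1 is not shown.

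**The concern.** The objective asks what TC Cream does to quality of life, and the trial is randomised against vehicle so that this can be answered. The answer is a difference between arms with an interval. A mean and its interval, even tabulated by arm, are not that estimate.

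Two things are at stake. The first is pre-specification. With no contrast written down, the analyst could choose after the fact between the week-8 score, change from baseline, percentage change or a cut-off on the DLQI bands, and a reader could not tell which choice came first. The second is precision. If baseline scores are available, a comparison that ignores them usually has a wider interval than the data allow.

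**Working it through.** **Step 1: does any planned method reach PDI and DLQI?**

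| Provision | What it needs | Do PDI/DLQI supply it? |
|---|---|---|
| t-test on response rates (synopsis; 9.2.4) | a responder definition | No, none is given |
| Success rule for all outcomes (5.1) | a clear/almost-clear grade and a two-grade drop | No, these are totals of 0 to 30, 0 to 45 or 0 to 90 |
| Summary of measurement data (9.2.4.1) | a numeric score | Yes, but it yields a mean, SD, range and CI for the mean, not a difference |

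No planned method gives a between-arm estimate for either score.

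**Step 2: the plan's own figure.** Section 9.1 gives 44 per arm and 90% one-sided power. It states no alpha, response rates or effect size, so the figure cannot be reproduced. It is not tied to PDI or DLQI. Only n = 44 per arm is carried forward.

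**Step 3: what baseline adjustment would gain.** Assumptions, none of them in the documents: SD = 1 at both baseline and week 8, no dropout, and a baseline to week-8 correlation ρ taken over a range.

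- Standard error of an unadjusted week-8 difference: √(2/44) = 0.2132 SD. The 95% half-width on 86 df is 0.424 SD.
- ANCOVA variance factor: (1 − ρ²) × [1 + 1/(2·44 − 4)] = (1 − ρ²) × 85/84. The second term is the price of estimating the slope. The half-width uses 85 df.
- Change-score variance factor: 2(1 − ρ).

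| ρ (assumed) | 1 − ρ² | × 85/84 | ANCOVA half-width (SD) | Against unadjusted 0.424 | Change-score half-width (SD) |
|---|---|---|---|---|---|
| 0 | 1.00 | 1.012 | 0.426 | marginally wider | 0.599 |
| 0.3 | 0.91 | 0.921 | 0.407 | 4% narrower | 0.501 |
| 0.5 | 0.75 | 0.759 | 0.369 | 13% narrower | 0.424 |
| 0.7 | 0.51 | 0.516 | 0.305 | 28% narrower | 0.328 |

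Example at ρ = 0.5: 0.369/0.424 = 0.87, which is 13% narrower.

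**Break-even.** Setting (1 − ρ²) × 85/84 = 1 gives ρ² = 1/85 and ρ = 0.108. Below about 0.11, adjustment costs a little precision.

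**Power for an assumed effect of 0.5 SD, two-sided 0.05.** Unadjusted: 64.0%. ANCOVA at ρ = 0.3, 0.5 and 0.7: 67.6%, 75.9% and 89.8%.

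The calculation omits the centre term. The synopsis lists two centres, so centre would use one further degree of freedom.

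**The case against.** **Tertiary endpoints may reasonably be described only.** In a phase IIb trial of 88 patients that is a defensible choice for a tertiary endpoint. But these two scores are the only measures named for the quality-of-life part of a secondary objective, and that objective concerns an effect of treatment. The rank limits how the result should be labelled. It does not remove the need for an estimate.

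**Section 5.1 may intend a responder analysis of every outcome.** On its face the success/failure sentence covers PDI and DLQI. If so, the defect is a missing responder threshold rather than a missing model. Either way there is no comparison that can be run as written.

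**The arms could still be compared from the summaries.** This largely stands. If the tables are by arm, which is the natural reading although section 9.2.4.1 does not say so, then the means, SDs and counts give an unadjusted difference and interval. A reader might infer that the trial could not separate TC Cream from vehicle or from regression to the mean. The documents do not support that: with randomised arms, regression to the mean is balanced in expectation. What is lost is a pre-specified estimate and some precision.

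**The gain is assumed.** This also stands. No correlation or SD is given. Entry is allowed at ISGA 2 and 1% BSA (section 3.3.4), and both scales have a floor at 0, so skewed scores and unequal SDs are plausible. A reader might also take the ρ = 0.5 case to mean that the plan forgoes the equivalent of 59 per arm (44/0.75 = 58.7). That compares ANCOVA with an unadjusted week-8 test that the plan does not specify, so it is not a loss against the current plan.

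**Conclusion.** The point holds and should be corrected. The plan specifies no usable between-arm comparison for the two measures that serve its quality-of-life objective. That conclusion rests on the text alone and on no assumed number.

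The size of the precision gain does rest on assumptions: equal SDs, complete data, and a correlation the documents do not give. Over ρ = 0.3 to 0.7 the interval is about 4% to 28% narrower than an unadjusted week-8 comparison, and there is no gain below about 0.11. These figures illustrate the choice of method and are not a measured deficiency of the trial.

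A reader might infer that week-0 PDI and DLQI scores are certainly available. Section 5.1 makes this likely, as does the objective's reference to improvement. But the schedule of events is not shown, so it should be confirmed. Nor is the remedy entirely free: it needs no extra patients or visits, but the PDI scoring and the missing-data rule have to be settled before it can be run.

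**What to change.** Add a paragraph to section 9.2.4.1 stating that:

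1. Week-8 PDI and DLQI totals are compared between arms by ANCOVA with arm, baseline score and centre. The result is the adjusted mean difference (TC minus vehicle) with a two-sided 95% CI. It is labelled supportive, and any p-value is nominal, because these are tertiary endpoints.
2. One PDI scoring, 0 to 45 or 0 to 90, is used throughout.
3. Missing week-8 totals are handled by a stated rule under ITT. Section 9.2.3 keeps dropouts in the ITT set, but the only related rule is that an unanswered PDI item scores 0. The text should say that this item rule does not extend to a questionnaire that was not completed, since that would give a total of 0, the best possible score.

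Keep the descriptive tables and state that they are by arm. In section 5.1, limit the success rule to the outcomes it fits. Confirm in the schedule of events that both questionnaires are completed at baseline and week 8.

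Cost: a paragraph of text and two decisions (PDI scoring and missing data), one degree of freedom for baseline and one for centre if there are two centres. If the schedule is as section 5.1 implies, no new data are needed. The primary analysis is unaffected.

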9.2.4.2 Safety Analyses

The safety data will be summarized with descriptive statistics.

10. ETHICAL AND REGULATORY REQUIREMENTS

10.1 Investigator Responsibilities

The investigator is responsible for ensuring that the clinical study is performed in accordance with the protocol, the current revision of the Declaration of Helsinki, current ICH and GCP guidelines, and applicable regulatory requirements. The investigator can delegate tasks to qualified designees.

10.2 Ethical Review

An investigator will not initiate a study without written approval from the Institutional Review Board (IRB). This protocol and the Informed Consent Form (ICF) will be reviewed and approved by the IRB prior to the initiation of the study. Any amendments to the protocol will also be reviewed by the IRB. A copy of the IRB's approval documentation will be included in the final report.

The IRB is constituted and operates in accordance with the principles and requirements described in the U.S. 21 CFR Part 56, and the ICH Harmonized Tripartite Guideline

10.3 Informed Consent

Written informed consent will be obtained from all patients or their legally authorized representative participating in this trial, as stated in the Informed Consent section of the Federal Regulations, Title 21, Part 50. If a patient's signature cannot be obtained, for all patients under the age of 18, the investigator must ensure that the patient's legally authorized representative signs the informed consent. Prior to signing the ICF, subjects will be allowed adequate time to consider the potential risks associated with their participation in the study. A copy of the signed ICF will be provided to the subject. Documentation of the consent process and a copy of the signed consent shall be maintained in the patient's medical record.

10.4 Confidentiality

All documentation collected by the sponsor or by the investigator will be kept confidential and remain the property of the sponsor.

10.5 Amendments and Protocol Revisions

Amendments to the protocol or the ICF will be submitted to the IRB for approval. Any modification to this protocol will be documented as a protocol revision or amendment, signed by the principal investigator and approved by the IRB before the revision or amendment may be implemented. The only circumstance in which the amendment may be initiated without regulatory approval is for a change necessary to eliminate an apparent and immediate hazard to the patient. In such cases, the investigator must notify the IRB in

Protocol Version: 00

writing within 10 working days after the implementation. PRIG confirms that any substantive major changes to the protocol will be notified to the FDA.

For amendments to the protocol that alter the study design after the study has been initiated, the investigator and/or the sponsor will decide whether the subjects' consent to continue participation is required. If an alteration is required to the ICF, subjects will be asked to sign the revised ICF at their next visit.

10.6 Study Termination

The sponsor (PRIG) reserves the right to terminate the study at any time.

11. MONITORING OF THE STUDY

11.1 On-Site Audits/Inspections

Representatives of the sponsor will visit the clinical research facility to conduct an audit of the study in compliance with regulatory guidelines and company policy. Such audits will require access to all study records, study medication, and source documents (CRFs) for inspection and comparison. The sponsor will provide sufficient notice to the clinical facility prior to the visit to allow adequate preparation for the audit.

Similar inspection procedures may also be conducted by agents of any regulatory body reviewing the results of this study in support of a New Drug Application. The clinical facility will immediately notify the sponsor if a regulatory agency contacts it regarding an upcoming inspection.

11.2 Monitoring

The sponsor or representative(s) of the sponsor may visit the study site to monitor the conduct of the study. The staff of the clinical facility will be available to assist the sponsor in answering any inquiries.

During these monitoring visits, the subjects' medical records, CRFs, and other study-related documents, including drug accountability records and study medications, will be made available for review.

12. ARCHIVES/RECORD RETENTION

The clinical facility will archive all study-related documents and retain test and reference products in accordance with applicable regulatory requirements.

If the investigator(s) relocate or, for any reason, withdraw from the study, the study

Protocol Version: 00

records must be transferred to an agreed-upon designee, such as another institution, another investigator, or to Psoriasis Research Institute of Guangzhou, Guangdong, China (PRIG). Records must be maintained in accordance with PRIG or FDA requirements.

